12.8.1. Definition of Serious Adverse Events

If an event is not an AE per definition above, then it cannot be an SAE even if serious conditions are met (e.g., hospitalization for signs/symptoms of the disease under study, death due to progression of disease, etc).

Serious Adverse Event (SAE) is defined as any untoward medical occurrence that, at any dose:

a. Results in death

b. Is life-threatening
 
NOTE:
 
The term 'life-threatening' in the definition of 'serious' refers to an event in which the subject was at risk of death at the time of the event. It does not refer to an event, which hypothetically might have caused death, if it were more severe.

c. Requires hospitalization or prolongation of existing hospitalization
 
NOTE:
 
 • In general, hospitalization signifies that the subject has been detained (usually involving at least an overnight stay) at the hospital or emergency ward for observation and/or treatment that would not have been appropriate in the physician's office or out-patient setting. Complications that occur during hospitalization are AEs. If a complication prolongs hospitalization or fulfills any other serious criteria, the event is serious. When in doubt as to whether "hospitalization" occurred or was necessary, the AE should be considered serious. • Hospitalization for elective treatment of a pre-existing condition that did not worsen from baseline is not considered an AE.

d. Results in disability/incapacity
 
NOTE:
 
 • The term disability means a substantial disruption of a person's ability to conduct normal life functions. • This definition is not intended to include experiences of relatively minor medical significance such as uncomplicated headache, nausea, vomiting, diarrhea,

influenza, and accidental trauma (e.g. sprained ankle) which may interfere or prevent everyday life functions but do not constitute a substantial disruption
e. Is a congenital anomaly/birth defect

f. Other situations:
 
 • Medical or scientific judgment should be exercised in deciding whether reporting is appropriate in other situations, such as important medical events that may not be immediately life-threatening or result in death or hospitalization but may jeopardize the subject or may require medical or surgical intervention to prevent one of the other outcomes listed in the above definition. These should also be considered serious. • Examples of such events are invasive or malignant cancers, intensive treatment in an emergency room or at home for allergic bronchospasm, blood dyscrasias or convulsions that do not result in hospitalization, or development of drug dependency or drug abuse

g. Is associated with liver injury and impaired liver function defined as:
 
 • ALT \geq 3xULN and total bilirubin* \geq 2xULN (>35% direct), or • ALT \geq 3xULN and INR** >1.5. 
* Serum bilirubin fractionation should be performed if testing is available. If fractionation is unavailable and ALT \geq 3xULN and total bilirubin \geq 2xULN, then the event is still to be reported as an SAE.
 
** INR testing not required per protocol and the threshold value does not apply to subjects receiving anticoagulants. If INR measurement is obtained, the value is to be recorded on the SAE form.

12.8.2. Recording of AEs and SAEs

AEs and SAE Recording:

 • When an AE/SAE occurs, it is the responsibility of the investigator to review all documentation (e.g., hospital progress notes, laboratory, and diagnostics reports) relative to the event. • The investigator will then record all relevant information regarding an AE/SAE in the eCRF • It is not acceptable for the investigator to send photocopies of the subject's medical records to PPD in lieu of completion of the GSK, AE/SAE eCRF page. • There may be instances when copies of medical records for certain cases are requested by PPD. In this instance, all subject identifiers, with the exception of the subject number, will be blinded on the copies of the medical records prior to submission of to PPD.

- The investigator will attempt to establish a diagnosis of the event based on signs, symptoms, and/or other clinical information. In such cases, the diagnosis will be documented as the AE/SAE and not the individual signs/symptoms.
- Subject-completed Patient Reported Outcomes questionnaires and the collection of AE data are independent components of the study.

12.8.3. Evaluating AEs and SAEs

Assessment of Intensity

The investigator will make an assessment of intensity for each AE and SAE reported during the study and will assign it to one of the following categories:

- Mild: An event that is easily tolerated by the subject, causing minimal discomfort and not interfering with everyday activities.
- Moderate: An event that is sufficiently discomforting to interfere with normal everyday activities
- Severe: An event that prevents normal everyday activities. - an AE that is assessed as severe will not be confused with an SAE. Severity is a category utilized for rating the intensity of an event; and both AEs and SAEs can be assessed as severe.
- An event is defined as 'serious' when it meets at least one of the pre-defined outcomes as described in the definition of an SAE.

Assessment of Causality

- The investigator is obligated to assess the relationship between placebo run-in or randomized treatment and the occurrence of each AE/SAE.
- A "reasonable possibility" is meant to convey that there are facts/evidence or arguments to suggest a causal relationship, rather than a relationship cannot be ruled out.
- The investigator will use clinical judgment to determine the relationship.
- Alternative causes, such as natural history of the underlying diseases, concomitant therapy, other risk factors, and the temporal relationship of the event to the placebo run-in or randomized treatment will be considered and investigated.
- The investigator will also consult the IB and/or Product Information, for marketed products, in the determination of his/her assessment.
- For each AE/SAE the investigator **must** document in the medical notes that he/she has reviewed the AE/SAE and has provided an assessment of causality.
- There may be situations when an SAE has occurred and the investigator has minimal information to include in the initial report to PPD. However, **it is very**

important that the investigator always make an assessment of causality for every event prior to the initial transmission of the SAE data to PPD.

- The investigator may change his/her opinion of causality in light of follow-up information, amending the SAE data collection tool accordingly.
- The causality assessment is one of the criteria used when determining regulatory reporting requirements.

Follow-up of AEs and SAEs

- The investigator is obligated to perform or arrange for the conduct of supplemental measurements and/or evaluations as may be indicated or as requested by PPD to elucidate as fully as possible the nature and/or causality of the AE or SAE.
- The investigator is obligated to assist. This may include additional laboratory tests or investigations, histopathological examinations or consultation with other health care professionals.
- New or updated information will be recorded in the originally completed eCRF.
- The investigator will submit any updated SAE data to PPD within the designated reporting time frames.

12.8.4. Reporting of SAEs to PPD

SAE reporting to PPD via electronic data collection tool

- Primary mechanism for reporting SAEs to PPD will be the electronic data collection tool
- If the electronic system is unavailable for greater than 24 hours, the site will use the paper SAE data collection tool and fax it to the Medical Monitor
- Site will enter the serious adverse event data into the electronic system as soon as it becomes available.
- The investigator will be required to confirm review of the SAE causality by ticking the 'reviewed' box at the bottom of the eCRF page within 72 hours of submission of the SAE.
- After the study is completed at a given site, the electronic data collection tool (e.g., InForm system) will be taken off-line to prevent the entry of new data or changes to existing data
- If a site receives a report of a new SAE from a study subject or receives updated data on a previously reported SAE after the electronic data collection tool has been taken off-line, the site can report this information on a paper SAE form or to the Medical Monitor by telephone.
- Contacts for SAE receipt can be found at the beginning of this protocol on the Sponsor/Medical Monitor Contact Information page.

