7.4.3.1. Time period and Frequency for collecting AE and SAE information

- Any SAEs assessed as related to study participation (e.g., protocol-mandated procedures, invasive tests, or change in existing therapy) or related to a GSK product will be recorded in the eCRF from the time a subject consents to participate in the study up to and including any follow-up contact.
- AEs and SAEs will be collected from the start of placebo run-in until the Follow-up visit (or the “End of Study” visit for subjects that discontinue study treatment early) (Section 7.4.3.3), at the time points specified in the Time and Events Table (Section 7.1).
- Medical occurrences that begin prior to the start of placebo run-in but after obtaining informed consent may be recorded on the Medical History/Current Medical Conditions Section of the eCRF.
- All SAEs will be recorded in the eCRF and reported to PPD within 24 hours, as indicated in [Appendix 8](#).
- Investigators are not obligated to actively seek AEs or SAEs in former study subjects. However, if the investigator learns of any SAE, including a death, at any time after a subject has been discharged from the study, and he/she considers the event reasonably related to the randomized treatment or study participation, the investigator must promptly notify PPD.
- NOTE: The method of recording, evaluating and assessing causality of AEs and SAEs plus procedures for completing and transmitting SAE reports to PPD are provided in [Appendix 8](#).

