12.9. Appendix 9: Liver Safety Required Actions and Follow up Assessments

Phase 3-4 liver chemistry stopping and increased monitoring criteria have been designed to assure subject safety and evaluate liver event etiology (in alignment with the FDA premarketing clinical liver safety guidance).

<http://www.fda.gov/downloads/Drugs/GuidanceComplianceRegulatoryInformation/Guidances/UCM174090.pdf>

Phase 3-4 liver chemistry stopping criteria and required follow up assessments

Liver Chemistry Stopping Criteria - Liver Stopping Event	
ALT-absolute	ALT \geq 8xULN
ALT Increase	ALT \geq 5xULN but <8xULN persists for \geq 2 weeks ALT \geq 3xULN but <5xULN persists for \geq 4 weeks
Bilirubin^{1,2}	ALT \geq 3xULN and bilirubin \geq 2xULN (>35% direct bilirubin)
INR²	ALT \geq 3xULN and INR>1.5, if INR measured
Cannot Monitor	ALT \geq 5xULN but <8xULN and cannot be monitored weekly for \geq 2 weeks ALT \geq 3xULN but <5xULN and cannot be monitored weekly for \geq 4 weeks
Symptomatic³	ALT \geq 3xULN associated with symptoms (new or worsening) believed to be related to liver injury or hypersensitivity
Required Actions and Follow up Assessments following ANY Liver Stopping Event	
Actions	Follow Up Assessments

 Immediately discontinue randomized treatment Report the event to PPD within 24 hours Complete the liver event eCRF and complete an SAE data collection tool if the event also meets the criteria for an SAE² Perform liver event follow up assessments Monitor the subject until liver chemistries resolve, stabilize, or return to within baseline (see MONITORING below) Do not restart subject with randomized treatment unless allowed per protocol and 	
 Viral hepatitis serology⁴ Only in those with underlying chronic hepatitis B at study entry (identified by positive hepatitis B surface antigen) quantitative hepatitis B DNA and hepatitis delta antibody⁵. Blood sample for PK analysis, obtained within 24 hour after last dose⁶ Serum creatine phosphokinase (CPK) and lactate dehydrogenase (LDH). Fractionate bilirubin, if total bilirubin \geq 2xULN

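### The paper back-up for SAE reports opens only after an outage of more than 24 hours, so an SAE already known when the outage starts can miss the protocol's own 24-hour limit

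*Protocol*

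**What the plan says.** Section 7.4.3.1 of the protocol sets the deadline: "All SAEs will be recorded in the eCRF and reported to PPD within 24 hours". The same sentence refers the reader to Appendix 8 for how this is done.

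Appendix 8, section 12.8.4, gives the routes:

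- In normal operation: "Primary mechanism for reporting SAEs to PPD will be the electronic data collection tool".
- In an outage: "If the electronic system is unavailable for greater than 24 hours, the site will use the paper SAE data collection tool", which is then faxed to the Medical Monitor.
- When the system returns: "Site will enter the serious adverse event data into the electronic system as soon as it becomes available".
- After the study is completed at a site and the tool has been taken off-line: "the site can report this information on a paper SAE form or to the Medical Monitor by telephone".

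The last route covers the period after site completion. It is not written for an outage during the study. Section 12.8.4 does not repeat the 24-hour limit or say that it takes precedence over the outage wait. Section 12.8.3 adds, for follow-up data, "The investigator will submit any updated SAE data to PPD within the designated reporting time frames", but Appendix 8 does not state those time frames.

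Appendix 9 sets the same limit for liver stopping events, "Report the event to PPD within 24 hours", and calls for the SAE data collection tool when such an event is also an SAE.

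**The concern.** A back-up route exists so that a deadline can be met when the main route fails. Here the trigger for the back-up (more than 24 hours without the system) is longer than the deadline it should protect (24 hours). A site that does exactly what Appendix 8 tells it to do can breach section 7.4.3.1, although that section points to Appendix 8 as the way to comply.

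What is at stake is the timeliness of individual SAE reports. Section 7.4.3.4 treats prompt notification of treatment-related SAEs as necessary for legal obligations and for subject safety. A serious liver event falling in an outage depends on the same back-up, because Appendix 8 offers no other.

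**Working it through.** No sample size, power or alpha figure is involved, so there is no stated figure to reproduce. The check compares two time limits.

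**Inputs**

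- Reporting limit: 24 hours (section 7.4.3.1).
- Paper trigger: system unavailable for more than 24 hours (section 12.8.4).
- Start of the reporting clock: not stated in section 7.4.3.1. I assume it is the moment the site learns of the SAE.
- Start of the outage count: not stated beyond the system being unavailable. I take the true start of the outage first and then the alternative.

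**Set-up.** Let the outage start at hour 0 and the site learn of the SAE at hour x, where a negative x means before the outage.

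- Deadline = x + 24.
- Paper opens just after hour 24.
- Paper time before the deadline = (x + 24) − 24 = x hours.

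**SAE learned before or at the start of the outage, not yet entered (x ≤ 0).** The time left when the outage begins is 24 + x hours. The report is late if the outage lasts longer than that.

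| Learned | Deadline (outage hour) | Paper opens (outage hour) | Result if 12.8.4 is followed literally |
|---|---|---|---|
| 10 h before (x = −10) | 14 | after 24 | Late if the outage exceeds 14 h; paper opens 10 + 24 = 34 h after awareness, 34 − 24 = 10 h late |
| 6 h before (x = −6) | 18 | after 24 | Late if the outage exceeds 18 h; paper opens 6 + 24 = 30 h after awareness, 6 h late |
| At onset (x = 0) | 24 | after 24 | Late if the outage exceeds 24 h, but paper opens only just past the deadline |

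An outage need not reach 24 hours to cause a miss. With x = −10, a 15-hour outage ends one hour after the deadline (15 − 14 = 1), and the paper route never opens at all.

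**SAE learned during the outage (x > 0).**

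- Learned 2 h in: deadline at hour 26, so 2 h of paper time.
- Learned 12 h in: deadline at hour 36, so 12 h of paper time.
- If the outage ends by hour 24, electronic entry is available again before x + 24.

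On this count every such SAE can be reported on time, but the margin is thin when x is small.

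**Alternative count.** If a site counts the outage from its own first failed entry at hour a, with a no earlier than x, paper opens after a + 24, which is no earlier than x + 24. An SAE learned during the outage is then also late whenever the outage runs past x + 24. Section 12.8.4 refers to the system being unavailable, which favours the true start, but does not settle how a site should count.

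**The case against.** The strongest reply is that nothing in section 12.8.4 prohibits paper, fax or telephone before 24 hours. The electronic tool is described as the primary mechanism, not the only one, and the outage sentence can be read as making paper compulsory after 24 hours without barring it earlier. Section 7.4.3.1 keeps the 24-hour duty with no exception for outages, so a site that faxes early satisfies both sections. This stands in part: the text contains no express prohibition. It also contains no instruction to go to paper early, and a site reading the appendix as its procedure would wait.

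A second reply is that other instructions may exist. Section 7 refers to further conduct detail in the Study Reference Manual, and section 12.8.4 refers to a contact page; neither is available here. This too stands in part. It cannot be said that sites have no route in practice, only that the protocol text, which names Appendix 8 as the method, gives none for the first 24 hours of an outage.

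A reader might infer three stronger things that the documents do not support:

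- That the two rules can never both be met. They can, for SAEs learned during an outage counted from its true start, and for earlier ones if the system returns before their deadline.
- That the IDMC's review would be compromised. Section 9.4.5 has the IDMC receive reports periodically, and a delay of hours in a single report is not shown to change any decision.
- That reporting of potential endpoint events to the Clinical Events Committee is delayed. Section 7.4.1 describes eCRF recording and submission of source documents for adjudication; section 12.8.4 concerns SAE reports to PPD.

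**Conclusion.** The point holds in a narrow form and is minor. The written trigger for the paper back-up is longer than the reporting window. Followed literally, it makes an SAE late if it was learned before or at the start of an outage, was not yet entered, and the outage outlasts its remaining time. Where the outage goes on past 24 hours, the lateness when paper opens is about the number of hours already used when it began.

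This rests on the clock starting at site awareness, on the outage being counted from its true start, and on the site taking section 12.8.4 at its word. The protocol gives no outage frequency, so the number of affected reports cannot be estimated. No estimand, power figure or analysis depends on it.

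**What to change.** Reconcile sections 7.4.3.1 and 12.8.4 by tying the back-up to the SAE's own deadline. For section 12.8.4, for example: if an SAE cannot be entered electronically in time to meet the 24-hour limit, the site sends the paper SAE form within that limit and enters the data electronically once the system is restored. Stating in section 7.4.3.1 what starts the 24-hour clock would remove the remaining ambiguity.

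The cost is one sentence in Appendix 8, a short clarification in section 7.4.3.1 and a notice to sites. No endpoint, visit, dose or analysis changes.

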12.9. Appendix 9: Liver Safety Required Actions and Follow up Assessments

Phase 3-4 liver chemistry stopping and increased monitoring criteria have been designed to assure subject safety and evaluate liver event etiology (in alignment with the FDA premarketing clinical liver safety guidance).

<http://www.fda.gov/downloads/Drugs/GuidanceComplianceRegulatoryInformation/Guidances/UCM174090.pdf>

Phase 3-4 liver chemistry stopping criteria and required follow up assessments

Liver Chemistry Stopping Criteria - Liver Stopping Event	
ALT-absolute	ALT \geq 8xULN
ALT Increase	ALT \geq 5xULN but <8xULN persists for \geq 2 weeks ALT \geq 3xULN but <5xULN persists for \geq 4 weeks
Bilirubin^{1,2}	ALT \geq 3xULN and bilirubin \geq 2xULN (>35% direct bilirubin)
INR²	ALT \geq 3xULN and INR>1.5, if INR measured
Cannot Monitor	ALT \geq 5xULN but <8xULN and cannot be monitored weekly for \geq 2 weeks ALT \geq 3xULN but <5xULN and cannot be monitored weekly for \geq 4 weeks
Symptomatic³	ALT \geq 3xULN associated with symptoms (new or worsening) believed to be related to liver injury or hypersensitivity
Required Actions and Follow up Assessments following ANY Liver Stopping Event	
Actions	Follow Up Assessments

 Immediately discontinue randomized treatment Report the event to PPD within 24 hours Complete the liver event eCRF and complete an SAE data collection tool if the event also meets the criteria for an SAE² Perform liver event follow up assessments Monitor the subject until liver chemistries resolve, stabilize, or return to within baseline (see MONITORING below) Do not restart subject with randomized treatment unless allowed per protocol and 	
 Viral hepatitis serology⁴ Only in those with underlying chronic hepatitis B at study entry (identified by positive hepatitis B surface antigen) quantitative hepatitis B DNA and hepatitis delta antibody⁵. Blood sample for PK analysis, obtained within 24 hour after last dose⁶ Serum creatine phosphokinase (CPK) and lactate dehydrogenase (LDH). Fractionate bilirubin, if total bilirubin \geq 2xULN


GSK Medical Governance approval is granted (refer to Appendix 10)
 
 If restart not allowed or not granted, permanently discontinue randomized treatment and may continue subject in the study for any protocol specified follow up assessments 
MONITORING:
 
For bilirubin or INR criteria:
 
 Repeat liver chemistries (include ALT, AST, alkaline phosphatase, bilirubin) and perform liver event follow up assessments within 24 hours Monitor subjects twice weekly until liver chemistries resolve, stabilize or return to within baseline A specialist or hepatology consultation is recommended 
For All other criteria:
 
 Repeat liver chemistries (include ALT, AST, alkaline phosphatase, bilirubin) and perform liver event follow up assessments within 24-72 hours Monitor subjects weekly until liver chemistries resolve, stabilize or return to within baseline 	
 Obtain complete blood count with differential to assess eosinophilia Record the appearance or worsening of clinical symptoms of liver injury, or hypersensitivity, on the AE report form Record use of concomitant medications on the concomitant medications report form including acetaminophen, herbal remedies, other over the counter medications. Record alcohol use on the liver event alcohol intake case report form 
For bilirubin or INR criteria:
 
 Anti-nuclear antibody, anti-smooth muscle antibody, Type 1 anti-liver kidney microsomal antibodies, and quantitative total immunoglobulin G (IgG or gamma globulins). Serum acetaminophen adduct HPLC assay (quantifies potential acetaminophen contribution to liver injury in subjects with definite or likely acetaminophen use in the preceding week [James, 2009]). Liver imaging (ultrasound, magnetic resonance, or computerised tomography) and /or liver biopsy to evaluate liver disease: complete Liver Imaging and/or Liver Biopsy eCRF forms.
---	---

- Serum bilirubin fractionation should be performed if testing is available. If serum bilirubin fractionation is not immediately available, discontinue randomized treatment for that subject if ALT \geq 3xULN **and** bilirubin \geq 2xULN.
- All events of ALT \geq 3xULN **and** bilirubin \geq 2xULN (>35% direct bilirubin) or ALT \geq 3xULN **and** INR>1.5, if INR measured which may indicate severe liver injury (possible 'Hy's Law'), **must be reported as an SAE (excluding studies of hepatic impairment or cirrhosis)**; INR measurement is not required and the threshold value stated will not apply to subjects receiving anticoagulants
- New or worsening symptoms believed to be related to liver injury (such as fatigue, nausea, vomiting, right upper quadrant pain or tenderness, or jaundice) or believed to be related to hypersensitivity (such as fever, rash or eosinophilia)
- Includes: Hepatitis A IgM antibody; Hepatitis B surface antigen and Hepatitis B Core Antibody (IgM); Hepatitis C RNA; Cytomegalovirus IgM antibody; Epstein-Barr viral capsid antigen IgM antibody (or if unavailable, obtain heterophile antibody or monospot testing); Hepatitis E IgM antibody

5. If hepatitis delta antibody assay cannot be performed, it can be replaced with a PCR of hepatitis D RNA virus (where needed) [Le Gal, 2005].
6. PK sample may not be required for subjects known to be receiving placebo or non-GSK comparator treatments. Record the date/time of the PK blood sample draw and the date/time of the last dose of randomized treatment prior to blood sample draw on the eCRF. If the date or time of the last dose is unclear, provide the subject's best approximation. If the date/time of the last dose cannot be approximated OR a PK sample cannot be collected in the time period indicated above, do not obtain a PK sample. Instructions for sample handling and shipping are in the SRM.

Phase 3-4 liver chemistry increased monitoring criteria with continued therapy

Liver Chemistry Increased Monitoring Criteria – Liver Monitoring Event	
Criteria	Actions

ALT \geq5xULN and $<$8xULN and bilirubin $<$2xULN without symptoms believed to be related to liver injury or hypersensitivity, and who can be monitored weekly for 2 weeks.
 
OR
 
ALT \geq3xULN and $<$5xULN and bilirubin $<$2xULN without symptoms believed to be related to liver injury or hypersensitivity, and who can be monitored weekly for 4 weeks.
	
 • Notify the PPD medical monitor within 24 hours of learning of the abnormality to discuss subject safety. • Subject can continue randomized treatment • Subject must return weekly for repeat liver chemistries (ALT, AST, alkaline phosphatase, bilirubin) until they resolve, stabilise or return to within baseline • If at any time subject meets the liver chemistry stopping criteria, proceed as described above • If ALT decreases from ALT \geq5xULN and $<$8xULN to \geq3xULN but $<$5xULN, continue to monitor liver chemistries weekly. • If, after 4 weeks of monitoring, ALT $<$3xULN and bilirubin $<$2xULN, monitor subjects twice monthly until liver chemistries normalize or return to within baseline.

References

